#### 8.1. PRIMARY EFFICACY ENDPOINT AND ANALYSIS

The primary endpoint is the percentage change from baseline to Week 2 in the EASI score. Baseline will be taken as the last non-missing measurement prior to administration of the first dose of IMP, this should be Day 1 for the primary endpoint.

The observed percentage change from baseline to Week 2 in the EASI score will be analysed for the FAS with an Analysis of Covariance (ANCOVA) model that includes baseline score as a covariate and treatment (ZPL521 or placebo). The treatment effect will be estimated with the difference between the least square means (LS means), defined as ZPL521 - placebo.

The ANCOVA analysis assumptions will be checked by evaluating the model residuals. A Shapiro-Wilks test will be performed on the residuals; a p-value > 0.1 will be considered proof of normality. If the Shapiro-Wilks p-value is  $\leq 0.1$ , the residual plot will be evaluated for symmetry. If the evaluation of residuals indicates a problem with the model assumptions, a transformation of the data will be considered, including a rank-transformation of the data.

The EASI score will be summarised by treatment and visit for the FAS with observed data. Summaries will present the descriptive statistics for baseline, change from baseline and percentage change from baseline data.

Patient profile plots by treatment group, of the percentage change from baseline in EASI score will also be presented. Note that only observed data will be included in these plots; i.e. no imputations will be used.

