#### 3.3. DETERMINATION OF SAMPLE SIZE

The sample sizes for Cohorts 1 and 2 are not based on formal statistical testing. Their sample sizes are considered sufficient to obtain suitable safety, tolerability and PK data prior to starting Cohort 3.

For Cohort 3 the sample size of 30 subjects has been determined on the basis of comparing the mean ZPL-5212372 Week 2 percentage change from baseline in the Eczema Area and Severity Index (EASI) score to that for placebo. With 20 subjects in the ZPL-5212372 group and 10 subjects in the placebo group, there is 80% power of obtaining a statistically significant result, assuming that there is an improvement of at least 30% with ZPL-5212372 compared to placebo and a standard deviation for the percentage changes from baseline between subjects of 30%. This is based on the analyses described and a 1-sided test at the 5% level of significance.

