### 6. GENERAL ASPECTS FOR STATISTICAL ANALYSIS

#### 6.1. GENERAL METHODS

All statistical tests for Cohort 3 will be 1-sided at the 0.05 level of significance and accompanied by a 2-sided 90% CI. There will not be any adjustments for multiple comparisons. No statistical testing will be performed with the data from Cohorts 1 and 2.

All summaries and listings will be presented by treatment group and by cohort. For Cohorts 1 and 2, adverse events and pharmacokinetic data will be presented by treatment group and BSA treated (10%, 40% and overall) to assess whether BSA impacts this data.

Only on-treatment records will be summarised for post-baseline visits, except follow-up, unless stated otherwise. A record is considered on-treatment if it is on or before the date of last study medication plus 1 day.

Continuous variables will be summarised using the number of observations (n), mean, standard deviation (SD), 95% Confidence interval (CI) of mean, median, minimum, and maximum. Geometric mean and coefficient of variation (CV) will be included for PK parameters, where appropriate. Categorical variables will be summarised using frequencies and percentages. The number of missing values will be presented in summary tables. The missing count will not include

SAP Version v2.0 Page 22 of 43

Date: 16th March 2017

subjects who have discontinued at earlier visits.

Unless otherwise specified, the estimated mean and median for a set of values should be printed out to 1 more decimal place than the original values, and standard deviations should be printed out to 2 more decimal places than the original values. The minimum and maximum should report the same number of decimal places as the original values. The coefficient of variation will always be reported as a percentage to 1 decimal place. Percentages will be displayed with 1 decimal place; except percentages will not be presented when the count is zero and 100% will be presented as an integer.

Unless stated otherwise, baseline will be defined as the last non-missing measurement prior to administration of the first dose of IMP.

In by-visit summary tables the baseline will be summarised using all available data, but also for each visit using only the baseline data from subjects with available data at the visit; hence the mean change from baseline will equal the mean visit value – mean baseline value.

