#### 6.4. STRATIFICATION

No stratification is used for the randomisation in Cohorts 1 and 2.

The randomisation for Cohort 3 is stratified by baseline EASI (≤20 or >20). This will be checked and any subjects who were misallocated to the wrong strata will be summarised according to the group they should have been assigned to. Misallocations will be listed.

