### 8.2.2. EASI Components

The 4 EASI component scores (erythema, oedema/papulation, excoriation and lichenification) will be summarised by treatment and visit for the FAS. Summaries will present the descriptive statistics for baseline, change from baseline and percentage change from baseline data.

Percent change from baseline to Week 2 for each EASI component will be analysed for the FAS with an ANCOVA model. The model will include baseline value and treatment. The treatment effect will be estimated with the difference between least square means (LS means), defined as ZPL521 - placebo. The estimate, standard error, 1-sided p-value, and 90% CI will be presented.

The analysis will be repeated for all other time points (Day 5, Day 8 [Week 1] and Day 10).

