### 8.2.7. Body Surface Area (BSA)

The percentage BSA affected will be summarised at each visit, including change and percentage change from baseline, by treatment group, using the FAS.

Change from baseline to Week 2 in the BSA will be analysed for the FAS with an ANCOVA model that includes baseline score, stratification variable (baseline EASI; ≤20 or >20) and treatment. The treatment effect will be estimated with the difference between the least square means (LS means), defined as ZPL521 - placebo. The estimate, standard error, 1-sided p-value, and 90% CI will be presented.

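### The EASI component ANCOVAs adjust only partially for the randomisation stratum; adding it as a factor costs one degree of freedom

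*SAP*

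**What the plan says.** SAP 6.4 says "The randomisation for Cohort 3 is stratified by baseline EASI", with the cut at 20. The Cohort 3 efficacy models then differ in how they use that factor:

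| SAP section | Endpoint | Terms besides treatment |
|---|---|---|
| 8.1, 8.1.1, 8.1.2 | EASI percentage change | continuous baseline EASI |
| 8.2.1 | EASI-50, EASI-75 | continuous baseline EASI |
| 8.2.2 | four EASI components | the component's own baseline |
| 8.2.3 | IGA response, IGA success | baseline IGA, stratum |
| 8.2.4 | pruritus NRS | baseline NRS, stratum |
| 8.2.6 | PGIC responder | stratum |
| 8.2.7 | BSA | baseline BSA, stratum |

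The primary analysis is a "model that includes baseline score as a covariate and treatment (ZPL521 or placebo". For the components, "The model will include baseline value and treatment", and that model is repeated at Days 5, 8 and 10. BSA has an "ANCOVA model that includes baseline score, stratification variable" and treatment. For EASI itself the stratum appears only as a subgroup (SAP 6.5, 8.1.2). The SAP gives no reason for the difference, and its list of changes from the protocol (SAP 12) does not mention the stratum.

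**The concern.** When randomisation is stratified, the arms are balanced on the stratum by design. If response also differs by stratum and the model leaves that difference in the residual, the model-based standard error is too large. The test then loses some power and becomes conservative. The usual remedy is to put the stratum in the model, and the SAP does so for four other groups of endpoints.

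The component models stand out. Every other Cohort 3 efficacy model contains either total baseline EASI or the stratum, and 8.2.2 contains neither. It covers 4 components at 4 time points, so 4 × 4 = 16 ANCOVAs. What is at stake is some precision in secondary analyses and consistency with the rest of the SAP, not bias.

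**Working it through.** **1. What the component baseline adjusts for.** Protocol Appendix 11 defines EASI as the sum over four regions of weight × (E + O + X + L) × extent. SAP 4.2 defines each component score with the same weights and extent grades, for example erythema = Σ weight × E × extent. Hence

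erythema + oedema/papulation + excoriation + lichenification = total EASI.

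A component's baseline is therefore one of four additive parts of the score that defines the stratum. It adjusts for the stratum in part, but not fully.

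**2. The SAP's own power figure.** Inputs from SAP 3.3 and 6.1:
- 20 active and 10 placebo subjects;
- "an improvement of at least 30% with ZPL-5212372 compared to placebo";
- "a standard deviation for the percentage changes from baseline between subjects of 30" percent;
- "All statistical tests for Cohort 3 will be 1-sided at the 0.05 level of significance".

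Noncentrality = 30 / (30 × √(1/10 + 1/20)) = 1/√0.15 = 2.582. By noncentral t the power is 80.9% with 28 df and 80.8% with 27 df (one covariate). This agrees with "there is 80% power of obtaining a statistically significant result".

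**3. Cost of one more degree of freedom.** Going from 27 to 26 df moves power from 80.83% to 80.76%. This ignores collinearity and any variance that the stratum explains.

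**4. Simulation, component-type model as written.** 8,000 trials per scenario. The documents give no baseline EASI distribution, block size or component variance, so these are assumptions: skewed baseline EASI between 12 and 48, permuted blocks of 3 within stratum, component baseline = 0.25 × EASI + noise of SD 2, residual SD 30 and effect 30 borrowed from the primary endpoint.

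| Severity effect on response | Power | Type I error |
|---|---|---|
| none | 80.2% | 5.4% |
| linear, 1 point per EASI point | 78.9% | 5.1% |
| 15-point step at EASI 20 | 78.4% | 5.2% |
| 30-point step at EASI 20 | 74.2% | 4.1% |

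Monte Carlo standard error is about √(0.8 × 0.2/8000) = 0.45 points for power and √(0.05 × 0.95/8000) = 0.24 points for type I error. The 4.1% is thus well below 5% beyond simulation noise; the 5.4% is not clearly above it.

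**5. Component-type model without and with the stratum** (further run):
- no severity effect: adding the stratum costs at most about 0.6 points;
- 10- to 15-point step: neutral to slightly positive;
- 30-point step: power rises from 74.3% to 78.1%, a gain of 3.8 points, and type I error moves from 4.0% to about 4.9%.

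**6. Primary model without and with the stratum** (same set-up as step 4):

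| Severity effect | Without | With |
|---|---|---|
| none | 80.1% | 79.4% |
| linear | 80.2% | 79.2% |
| 15-point step | 79.4% | 79.2% |
| 30-point step | 76.7% | 79.2% |

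A separate run gave 79.6% without and 79.7% with the stratum at a 20-point step, so break-even is at about 20 points. Type I error was 4.6–5.4% without and 5.0–5.2% with the stratum.

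**The case against.** The strongest objection concerns the primary endpoint, and it stands. A reader might infer that the primary model ignores the stratification. It does not: the stratum is a dichotomy of baseline EASI, which is already a continuous covariate. The model also matches Protocol 8.5.1. The same holds for EASI-50 and EASI-75.

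A reader might also infer from step 6 that the stated 80% power is at risk. The documents do not support that. The fall below 80% arises because the step was added on top of a residual SD of 30. SAP 3.3 defines 30 as the SD of percentage changes between subjects, so a severity step belongs inside it. With half the subjects in each stratum (an assumption) and a 30-point step, the within-stratum SD would be √(900 − 0.25 × 900) = 26.0. With total within-arm SD held at 30, simulation gives the primary model as written 81.3%, 85.7% and 89.2% power for steps of 15, 30 and 40 points, so it never drops below 80%.

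On the components, it would be too strong to say that the stratum goes unadjusted, as step 1 shows. It is also fair that a 30-point step equals the whole assumed treatment effect, and nothing in the documents suggests one. What remains is that 8.2.2 departs from the SAP's own pattern without a reason, and that correcting it costs almost nothing.

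**Conclusion.** The point holds for the EASI component ANCOVAs, as a minor one. They adjust for the randomisation factor only through part of the stratifying score. Adding the stratum costs under 1 power point if response is unrelated to severity, is about neutral for a 10- to 15-point step, and gains about 4 points for a 30-point step, where it also brings type I error from about 4% back to about 5%. Omission errs towards conservatism; no material inflation of type I error was found.

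These sizes rest on assumed step sizes, baseline distribution, block size and component-to-total relation, and on borrowing the primary endpoint's SD and effect for the components. They show direction and order of magnitude only.

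For the primary model, adding the stratum is optional: neutral or about 1 point worse below a step of about 20 points, and better only above that.

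**What to change.** In SAP 8.2.2, add the randomisation stratum (baseline EASI ≤20 or >20) as a factor beside treatment and the component's baseline value, for Week 2 and for the Day 5, 8 and 10 repeats. This is the form already used in SAP 8.2.4 and 8.2.7. The cost is one sentence of SAP text and one degree of freedom per model, with no new data.

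SAP 8.1 and 8.2.1 can stay as they are. A line stating that continuous baseline EASI carries the stratification there would remove any doubt that the difference is deliberate.

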### 8.1.1. Sensitivity Analyses of the Primary Endpoint

The robustness of the primary analysis will be evaluated by repeating the primary analysis with

SAP Version v2.0 Page 28 of 43

Date: 16th March 2017

the per-protocol analysis set.

In addition, the following sensitivity analyses will be conducted using the FAS:

- an analysis where missing values will be imputed using MCMC multiple imputation methods (see Section 6.2.1). These imputations will be performed separately within each treatment group.
- an analysis using a worst case imputation for missing data considered as 'informative'.
   Missing data will be reviewed by the study team to identify situations where the
   missingness is considered informative; e.g. subject withdrew for lack of efficacy. In these
   situations the Week 2 score will be taken as equal to the worst score recorded for either
   treatment group. For the 'non-informative' values the MCMC imputed values will be
   used. Note, the worst case imputation i.e. worst score, will occur after the MCMC values
   have been generated.
- an analysis using an LOCF method for handling missing data

In addition, the EASI score will be summarised by treatment and visit for the FAS with MCMC imputation data. For this summary, the mean of the imputed data for a subject is used in the calculation. Hence when multiple imputations are performed for the analysis, a missing data point will be estimated with the mean of the multiple different imputations; this individual mean will be used to calculate the overall treatment summary statistics.

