#### **4.8 Subject Withdrawal and Replacement**

Subjects will be discontinued from the investigational product and potentially from the study in the following circumstances:

- 1 Enrollment in other clinical studies involving investigational products or enrollment in other types of clinical research judged not to be scientifically or medically compatible with this study.
- 2 The subject requests to be discontinued from the study.
- 3 Use of prohibited concomitant medications.
- 4 Sponsor decision to stop the study or to stop the subject's participation in the study for medical, safety, pharmacokinetic or regulatory, or other reasons consistent with applicable laws, regulations, and good clinical practices (GCP).
- 5 A severe or serious adverse event occurs that the investigator considers is related to study drug.

- 6 Any criteria for laboratory safety or vital sign values of Potential Clinical Concern (Appendix 1).
- 7 Any criteria for Hepatic Safety (Appendix 2).
- 8 Any criteria for ECG Values of Potential Clinical Concern (Appendix 3).

Subjects may have their study drug discontinued if they have abnormal laboratory results which are considered to be clinically significant as assessed by the investigator. This decision should be made in the best interest of the subject and follow up should be conducted using standard clinical practices. Subjects may also be temporarily discontinued from study drug while AEs and/or laboratory test abnormalities are being investigated and/or at the request of the sponsor's CMO. The investigator should discuss with Ziarco's CMO any subject for whom temporary or permanent discontinuation of study drug is being proposed. Subjects who discontinue early from the study should be asked to complete all the efficacy and safety assessments scheduled for the end of study assessment.

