### **8.5.1 Primary Endpoint**

The primary efficacy endpoint is the percentage change from baseline to Week 2 in the EASI score.

The primary analysis will be performed using the FAS. A secondary analysis of the primary endpoint may be conducted using the PP analysis set, if sufficiently different to the FAS, to examine the robustness of the primary analysis results.

The percentage changes from baseline in the EASI score at Week 2 will be summarized by treatment group and analysed by ANCOVA. The difference between treatment groups in the percentage changes from baseline will be estimated, along with its 90% confidence interval. Baseline will be included as a continuous covariate in addition to treatment. This analysis will be repeated for the sensitivity analyses where different approaches will be adopted for handling missing data.

Sub-groups will include the levels of the stratification factor. Other sub-groups will be specified in the SAP.

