### 6.3. VISIT WINDOWS

There is no requirement for visit windows for Cohorts 1 and 2 as subjects will remain in the CRU for the duration of the study, so all assessments will be presented and analysed according to the visit assessment recorded.

For Cohort 3, all assessments will be presented and analysed according to the visit assessment recorded. Due to the short study duration visit windows will not be used. If possible, any early termination visits will be assigned to the closest study visit if they are on-treatment. Prior to database lock the data will be reviewed to identify any outlying visits and make decisions on how to deal with any issues. All decisions will be documented prior to database lock.

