### 8. EFFICACY

As Cohort 1 includes healthy volunteers no efficacy data will be collected. Though some efficacy assessments are included for Cohort 2 the data will only be listed and no formal comparisons will be made between the treatment groups. Consequently efficacy will only be assessed for Cohort 3. Hence the following analyses apply to Cohort 3 data.

The observed data summaries for all efficacy endpoints, except PGIC, will only use 'on-treatment' records (i.e. on or before the date of last study medication plus 1 day) for all visits, except baseline and follow-up.

For all ANCOVA analyses the treatment least square means (LS means) and LS mean standard errors, treatment difference estimate, standard error, 1-sided p-value, and 90% CI will be presented. The corresponding SAS ANCOVA output will also be outputted for internal statistical review.

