### 8.2. SECONDARY ENDPOINTS AND ANALYSIS

#### 8.2.1. EASI-50 and EASI-75

The proportion of subjects who achieve an EASI-50 response will be summarised in the FAS with counts and percentages by treatment group at each visit. The number of missing values will also be presented.

An exact logistic regression analysis will be performed at Week 2. The model will include treatment and baseline EASI score. The odds ratio, p-value and associated exact 90% CI will be presented. Subjects with missing responses will be counted as non-responders.

The proportion of subjects who achieve an EASI-75 response will be analysed in the same way as described for the EASI-50.

SAP Version v2.0 Page 29 of 43

Date: 16th March 2017

The cumulative proportion of subjects achieving a  $\ge x\%$  reduction in EASI at Week 2 will be plotted against x, with different lines for each treatment group. Subjects with missing data will be regarded as having the worst change from baseline and labelled as such on the plot. Horizontal reference lines will be drawn that relate to the 0, 25, 50 and 75% reductions in EASI scores.

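### The worst-case sensitivity analysis imputes one common EASI score although the endpoint is percentage change, so the penalty depends on each dropout's baseline and is not always a worst case

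*SAP*

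**What the plan says.** SAP 8.1 defines the endpoint: "The primary endpoint is the percentage change from baseline to Week 2 in the EASI score". It is analysed by ANCOVA with baseline score and treatment. If the residual check shows a problem, "a transformation of the data will be considered, including a rank-transformation of the data".

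SAP 8.1.1 adds a worst-case run. The study team decides which missing values are informative, for example after withdrawal for lack of efficacy. In these "situations the Week 2 score will be taken as equal to the worst score recorded for either" treatment group. The same bullet then repeats that it is the worst score, applied after the MCMC values have been generated. It does not say which visits count as recorded.

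For the cumulative plot in SAP 8.2.1 the convention differs: "Subjects with missing data will be regarded as having the worst change from baseline and labelled as such on the plot". That shows the alternative wording is available in this SAP. It does not show that it was intended in 8.1.1.

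**The concern.** The imputation is made on the score scale and the analysis on the percentage-change scale. Imputing a score and then deriving the endpoint is coherent in itself. The difficulty is giving every informative dropout the same score: the derived endpoint is then inversely related to that patient's own baseline, which says nothing about why the patient left.

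Of the planned analyses of the primary endpoint, this is the only one that penalises informative dropout. It is meant to show whether such dropout could overturn the primary result. As written, its answer depends partly on the baselines the dropouts happen to have. Some of them receive a value milder than a change already seen in the trial. If only Week 2 scores count, a dropout whose baseline exceeds W is imputed as improved.

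**Working it through.** **Planning figure.** SAP 3.3 gives 20 active and 10 placebo subjects, difference 30, SD 30, one-sided 5%. The standard error is 30 × √(1/20 + 1/10) = 11.6, and 30/11.6 = 2.58. The noncentral t distribution gives 80.9% power on 28 df, or 80.8% on 27 df for the ANCOVA. The stated 80% is reproduced.

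**Imputed endpoint.** This is 100 × (W/b − 1), where b is the Day 1 EASI, 12 to 48 (Protocol 4.2 and 6.4.1). The documents give no W, so a range is shown:

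| W | b = 12 | b = 20 | b = 30 | b = 40 | b = 48 |
|---|---|---|---|---|---|
| 30 | +150% | +50% | 0% | −25% | −37.5% |
| 36 | +200% | +80% | +20% | −10% | −25% |
| 40 | +233% | +100% | +33% | 0% | −17% |
| 48 | +300% | +140% | +60% | +20% | 0% |

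Against the planning SD of 30, +233% is 233/30 = 7.8 SDs above no change. Negative entries require W below the dropout's own baseline. That cannot happen if baseline scores count as recorded.

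**When the value is too mild.** If w is the worst recorded percentage change, the imputed value is milder than w whenever b > W/(1 + w/100). With w = +50%, the threshold is 24 for W = 36 and 32 for W = 48, both inside the eligible range.

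**Effect of the dropout's baseline alone.** This simulation has one active dropout, a true effect of −30 and W taken from Week 2 scores (4000 trials per baseline). Assumed: placebo mean −20%, lognormal baseline with median 21 and log-SD 0.35, clipped to 12–48.

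| Dropout baseline | Median imputed value | Mean difference (SE) | Significant |
|---|---|---|---|
| 12 | +197% | −17.4 (21.7) | 9% |
| 20 | +80% | −22.6 (15.1) | 41% |
| 30 | +19% | −25.7 (12.4) | 65% |
| 40 | −11% | −27.4 (11.6) | 73% |
| 48 | −26% | −28.0 (11.4) | 78% |

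Imputing the worst percentage change instead gives a median of about +27% and significance in 63–68% of trials at every baseline.

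**Several dropouts, both readings.** These are 4000 trials per scenario (Monte Carlo SE at most 0.8 points) with the SAP 3.3 inputs and EASI capped at 72 (Protocol Appendix 11). The following are assumed and not in the documents; ranges tested are in brackets:

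- Baseline lognormal, median 21, log-SD 0.4 (0.25–0.6), limited to 12–48.
- Placebo mean −15% (0 to −30%).
- Means at Days 5, 8, 10 and 15 equal to 30, 55, 70 and 100% of the Week 2 mean; SDs 21, 25.5, 27 and 30; between-visit correlation 0.7 (0.5–0.9).
- Random dropouts leaving after Day 8, and no other missing data.

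The any-visit reading takes the worst score over baseline and all on-treatment visits. The comparator is the worst percentage change over all on-treatment post-baseline visits. One-sided significance without transformation:

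| Scenario | Written rule, Week 2 | Written rule, any visit | Worst % change |
|---|---|---|---|
| No effect, one placebo | 16% | 17% | 12% |
| No effect, two placebo | 38% | 43% | 24% |
| No effect, two active + one placebo | 1% | 1% | 2% |
| True −30, one active | 44% | 32% | 62% |
| True −30, two active | 18% | 8% | 38% |
| True −30, two active + one placebo | 34% | 21% | 57% |

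- Over the input ranges (1000 trials each): two placebo 30–38% / 36–45% vs 22–28%; two active 15–27% / 7–15% vs 33–39%; two active plus one placebo with true −30, 30–43% / 17–31% vs 52–58%.
- Median imputed value: +77 to +104% / +116 to +130% vs +44 to +54%.
- Milder than the worst recorded on-treatment change: 24–31% / 15–16% of imputed values. Imputed as improved: 3–8% / 0%.

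**With ranks.** Response and baseline are both ranked when the residual Shapiro-Wilk p ≤ 0.1. The check flags the written rule in 53–82% / 64–96% of trials. Two placebo dropouts, no effect: 22% / 21% vs 24%. Two active, true −30: 51% / 50% vs 44%. Two active plus one placebo: 3% / 3% vs 2% with no effect, and 63% / 63% vs 60% with true −30.

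**The case against.** **The SAP's own remedy may cure it.** Protocol 8.5.1 says "This analysis will be repeated for the sensitivity analyses where different approaches will be adopted for handling missing data", so the residual check plausibly carries over. It would flag most of these trials, and with ranks the written rule does as well as the alternative, or slightly better. This stands as arithmetic. It does not settle the matter: the SAP commits only to considering a transformation, after a visual judgement of symmetry, and 8.1.1 does not mention the check.

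**Random dropout is not the trigger.** The rule is for informative dropout. If dropouts come from the worse half of their arm, two placebo dropouts give 23% / 29% vs 14%, lower than the leading figures. Two active dropouts give 22% / 12% vs 45%. The levels move, but the gap remains.

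**A worst case should be harsh, and any one-sided imputation shifts the result.** Both are true. The alternative still gives 24% with two placebo dropouts, and dropouts in the 2:1 ratio cause no false-positive inflation. But harshness set by baseline is not a consistent stress test, and some values are too mild.

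**Few values may need the rule.** Under Protocol 4.8 early leavers "should be asked to complete all the efficacy and safety assessments scheduled for the end of study assessment". Under SAP 6.3, where possible, "any early termination visits will be assigned to the closest study visit if they are on-treatment", which SAP 8 defines as "on or before the date of last study medication plus 1 day". EASI-50 and EASI-75 also count missing as non-response whatever the baseline, though these are secondary endpoints. This limits the reach but does not repair the rule. Lack-of-efficacy withdrawals are not replaced, and one active dropout already costs 62 − 44 = 18 or 62 − 32 = 30 points of power relative to the alternative.

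**Conclusion.** The point holds. The dependence on 1/baseline is algebra and needs no assumption. The excessive penalty at low baselines follows from the 12–48 eligibility range. Values milder than the worst recorded change depend on the data but are common under both readings. Imputed improvements arise only if recorded means Week 2 alone.

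The size of the effect on significance rests on the assumed baseline distribution, placebo response, visit correlation and dropout pattern, and on no transformation being applied. Its direction is the same over the ranges tested. If ranks are used, the distortion nearly disappears.

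Reach is limited to the worst-case run. The primary, per-protocol, MCMC and LOCF analyses and the 80% power are unaffected. It should be corrected before database lock, because otherwise the result of this run depends on dropout baselines and on a transformation chosen after the data are seen.

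**What to change.** Replace the imputation sentence in SAP 8.1.1, keeping its place after the MCMC step, with:

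> The Week 2 percentage change will be taken as the worst (largest) percentage change from baseline recorded at any on-treatment post-baseline visit in either treatment group.

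Add:

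> The residual check in Section 8.1 applies to this analysis.

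Every informative dropout then gets the same value on the analysed scale, and the visits that count are stated. Using all on-treatment visits rather than Week 2 alone matters: in the simulations 5–7% of dropouts had an earlier change worse than the worst observed Week 2 change (2–13% over the ranges). With this wording the imputed value cannot be milder than an on-treatment change the dropout had already recorded.

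The cost is two sentences and one line of code. There are three downsides. The imputed value is usually less extreme than under the present rule. The result still shifts towards the arm with fewer informative dropouts. If ranks are used anyway, the change gains little and costs a few points of power (two active dropouts: 44% against 50–51%).
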